3.2. Outcomes

3.2.1. Primary outcome

The primary outcome is to identify factors (genetic, immunological and environmental) that contributes to the observed heterogeneity in immune responses (individual and population levels).

- To characterize the naturally occurring genetic and variability of human response using whole genome sequencing and SNPs haplotyping.
- To determine and measure cytokine/chemokine stimulated by 40 pattern-recognition receptors agonists (PRR agonists) or immune stimulators
- To characterize commensal microbiota (nasal swab and stools samples) in the study population
- To evaluate the metagenomic architecture of the population based on sequence analysis of bacterial, fungal and viral populations in fecal and nasal samples.
- To associate immune response with nutrition data.
- To associate immune phenotype variance with genetic polymorphisms and enterotype

3.2.2. Secondary outcomes

The secondary outcome is the determination of genotype-to-phenotype associations at a mechanistic level.

3.2.3. Estimated calendar

- First enrolment (FSFV: first subject first visit V0): September 2012
- Duration of the enrolment : about 12 months
- Last enrolment: around August 2013
- Total duration of the study follow-up (FSFV–LSLV): 14 months

- Last visit (LSLV: last subject last visit V2): October 2013
- Duration of participation for one subject: max 8 weeks (56 days) for subject performing V2 with or without biopsy at V1 and max 2 weeks (14 days) for subject performing V1 only
- Total duration of the study (results analysis): 5.5 years
- Results analysis: 2018

4. STUDY POPULATION

4.1. Description of study population

1000 healthy donors will be included in the study by the following center:

- Biotrial Rennes

Subjects will be stratified according to gender with a 1:1 ratio (with 500 subjects by gender); age (5 decades of age: [20, 29], [30, 39], [40, 49], [50, 59] and [60, 69] years, with 200 subjects per strata), and V2 (100 subjects performing V2 per decade with 50% female and 50% male) to ensure 100 subjects per gender per decade strata..

Subjects with biopsy (up to 500 from subjects performing V2) will be selected after draw by lot at visit V1.

E.g.: decade strata [20, 29]: 100 males and 100 females

Decade	Age	Gender	Biopsy	V1	V2
1	20 - 29 (200)	males (100)	Yes*	50	50
			No	50	0
		females (100)	Yes*	50	50
			No	50	0
2	30 - 39 (200)	males (100)	Yes*	50	50
			No	50	0
		females (100)	Yes*	50	50
			No	50	0
3	40 - 49 (200)	males (100)	Yes*	50	50
			No	50	0
		females (100)	Yes*	50	50
			No	50	0
4	50 - 59 (200)	males (100)	Yes*	50	50
			No	50	0
		females (100)	Yes*	50	50
			No	50	0
5	60 - 69 (200)	males (100)	Yes*	50	50
			No	50	0
		females (100)	Yes*	50	50
			No	50	0
TOTAL SUBJECTS				1000	500

* Up to 500 biopsies will be performed. In case less biopsy is performed, 500 subjects will even though performed V2 without biopsy at V1.

As in any genetic association study, it is imperative to minimize the presence of population variability in the study cohort (i.e. genetic heterogeneity due to basic population genetic differences). It is thus essential to restrict the recruitment to individuals belonging to the same ethnic background. As the study will be conducted in France, it will be limited to Metropolitan French origin individuals for 3 generations. Consequently, the subjects' ancestry has to be metropolitan French's for 3 generations (i.e. the subject, his/her parents and his/her grandparents).

To avoid hormonal cyclic fluctuations observed in females during the peri-menopausal period, only pre- and post-menopausal women will be included.

4.2. Inclusion criteria

1. Subjects considered as healthy by the investigator based on medical history, clinical examination, laboratory results and ECG (blood sampling for laboratory assessments and ECG should be done at V0 and only after signed informed consent).
2. Subjects who, according to the investigator, can and will comply with the requirements of the protocol and are available for all scheduled visits at the investigational site.
3. Healthy male or female aged between 20 and 69 (included) years
4. Metropolitan French origin for 3 generations
5. $18.5 \leq \text{BMI} \leq 32 \text{ kg/m}^2$ (Appendix 18.6)
6. Ability to give their informed consent in writing
7. Must understand spoken and written French
8. Affiliated to the French social security or assimilated regimens
9. Registered on the French "Fichier des Volontaires se prêtant à la Recherche Biomédicale (VRB)"

4.3. Non-inclusion criteria

1. Subjects who cannot participate according to their status on the registry mentioned at Art L. 1121-16 of the French Public Health Code
2. Participation in another clinical study in the last 3 months in which the subject has been exposed to an investigational product (pharmaceutical product or placebo or medical device) or concurrent participation in another clinical study during the study period
3. Relatedness to previously recruited individuals in the study cohort
4. Travel in (sub-)tropical countries within the last 3 months
5. For women: pregnant or breastfeeding or intending to become pregnant or peri-menopausal*

**Peri-menopausal women as defined by menstrual irregularity: either a change in the menstrual cycle length of more than seven days (early perimenopause) or two or more missed periods with an interval of 60 days or more between periods (late perimenopause) (Stages of Reproductive Aging Workshop, STRAW)(11)*

6. Any physical exercise within the last 8 hours before inclusion (V1) and before (V2)

-
7. Subjects following a special diet for medical reasons as prescribed by a GP or dietician (e.g. calorie restricted or weight-loss diet for significant overweight, cholesterol lowering diet or subjects suffering from any clinically diagnosed food allergy or intolerance)
 8. Alcohol abuse (more than 50 g of pure ethanol per day: for example, more than 4 x 150 mL glasses of wine, more than 4 x 250 mL glasses of beer, more than 4 x 40 mL glasses of high alcohol content drinks)
 9. Illicit drug use or substance abuse within 3 months prior to inclusion
 10. Presence of evidence of neurological or psychiatric diagnoses which, although stable, are deemed by the investigator to render the potential subject unable/unlikely to participate in the study satisfactorily.
 11. Severe/chronic/recurrent pathological conditions, among them:
 - 11.1. Past or present diagnosed cancer, lymphoma, leukemia to the exception of:
 - Persons with a history of cancer who are disease-free without treatment for 5 years or more
 - Women who are disease free for 3 years or more after treatment for breast cancer and receiving long-term prophylactic tamoxifen
 - Cutaneous or cervical basal cell carcinoma
 - 11.2. Personal history of organ transplant
 - 11.3. Congenital or acquired immune deficiency (any confirmed or suspected immunosuppressive or immunodeficient condition, including history of HIV infection)
 - 11.4. Personal history of auto-immune diseases requiring or having previously required treatment (e.g. Rheumatoid Arthritis, Systemic Lupus Erythematosus, Sarcoidosis, Ankylosing Spondylitis, Autoimmune Hemolytic Anemia, Autoimmune Thrombocytopenic Purpura, Crohn's Disease, Psoriasis, Scleroderma, Wegener's Granulomatosis, Type I Diabetes, Thyroiditis,....)
 - 11.5. Splenectomy
 - 11.6. Acute or chronic, clinically significant, as determined by the investigator, pulmonary, cardiovascular, hepatic or renal functional abnormality, as determined by physical examination or laboratory screening tests
 - 11.7. History of clinically significant, as determined by the investigator, neurological disorder or seizures
 - 11.8. Infectious diseases:
 - Chronic infection (e.g. HIV, HBV, HCV...) or current acute infection or past acute infection based on investigator's judgment within the last 3 months,
 - Presence of a rectal temperature $\geq 38.4^{\circ}\text{C}$, or axillary temperature $\geq 37.5^{\circ}\text{C}$, or intra-auricular temperature $\geq 38.4^{\circ}\text{C}$, or buccal temperature $\geq 38^{\circ}\text{C}$ on the scheduled date of inclusion,
 - Subject receiving (currently or in the last 3 months) antibiotics, intestinal, nasal or respiratory antiseptics.
 - 11.9. Severe High Blood Pressure defined as systolic BP ≥ 160 mmHg and/or diastolic BP ≥ 100 mmHg (AHA stage 2 HBP). Treated and controlled HBP is allowed.
 - 11.10. Type II diabetes mellitus requiring treatment with any medication. Diabetes mellitus treated by exercise and diet control only is permitted.
 - 11.11. Chronic renal impairment as defined by Renal Insufficiency: GFR < 60 mL/min/1.73 m² (National Kidney Foundation (2002) (8))

-
- 11.12. Chronic bone disease as treated by biphosphonates
 - 11.13. Treated depression or any evidence of overt depressive episode during medical examination and interview
 - 11.14. Any significant disorder of coagulation or treatment with warfarin derivatives or heparin or antiplatelet medications within 2 months preceding inclusion.
 - 11.15. Dermatologic conditions: any current dermatological disorder that is severe enough to prevent the skin biopsy (e.g. eczema, psoriasis, acute or chronic dermatitis)
 - 11.16. Severe acute/chronic allergy
 - Severe Asthma defined as asthma requiring a combination of two or more controller therapies (e.g. medium or high dose inhaled glucocorticosteroid and long-acting inhaled beta-2 agonist) or requiring oral glucocorticosteroids (GINA(3)),
 - Severe food allergy, as defined by history of giant urticaria, Quincke edema or anaphylactic shock,
 - Severe insect bite allergy with history of giant urticaria, Quincke edema or anaphylactic shock,
 - Atopic dermatitis treated with medication.
 12. Chronic administration (defined as more than 14 days) of immunosuppressants or other immune-modifying drugs within the 6 months prior to the inclusion. For corticosteroids, this will mean a dose equivalent to 20 mg/day of prednisone or equivalent for > 2 weeks (inhaled and topical steroids allowed)
 13. Chronic administration of NSAIDs, including aspirin: prolonged intake (> 2 weeks) within 6 months before study or any intake within the 7 days preceding skin biopsy [exception for low dose aspirin: : maximum 250mg/daily, see 8.1]
 14. Receipt of any vaccination 3 months before the inclusion or planning to receive any vaccination during the study
 15. Receipt of blood products or immunoglobulins within 3 months prior the inclusion or planning to receive blood products or immunoglobulins during the study
 16. Hemoglobin measurement less than 10.0 g/dL for women and less than 11.5 g/dL for men
 17. Platelet count less than 120.000/mm³
 18. ALAT and/or ASAT > 3 times the upper limit of the norm (ULN)
 19. Allergy to lidocaine

5. INVESTIGATOR CENTERS

The study will be conducted in Biotrial's clinical pharmacology unit (CPU) in Rennes:

Biotrial Rennes: [name]

The global capacities of 150 beds and the 250 employees across the 2 hospital based CPU's allows Biotrial to perform around 80 healthy volunteer studies per year since its creation in 1989 across a wide spectrum of therapeutic areas.

Studies are conducted according to GCP-ICH guidelines and common Standard Operating Procedures in the 2 CPUs certified by AFSSAPS (authorizations 05001M, 1001 OM, AFSSAPS). Medical supervision of the subjects is ensured by 8 full-time investigators supported by a full clinical team composed of study nurses and laboratory technicians. In

addition, Phase I healthy volunteers studies are performed under the control of an experienced Medical Director and the collaboration of the Medical Scientific and Quality Affairs department.

Each site has access to a local laboratory which is compliant with GBEA standard (French law) and certified Cofrac (French Accreditation Committee) NF17025 and to state-of-the-art equipment for ECG recording or vital signs collection.

Due to its significant experience in healthy volunteer studies, Biotrial has elaborated a large volunteer database of more than 36 000 active volunteers. Existing processes for recruitment (advertising, information of the volunteers) are designed to allow efficient subject enrolment.

6. PRACTICAL ASPECTS OF THE RESEARCH

6.1. Overall study organization

The recruitment of the healthy donors will be done in the investigator center: Biotrial's clinical pharmacology unit (CPU) in Rennes.

The first step of the study will be the selection of the subjects based on study eligibility criteria then up to 3 visits will be planned for each included subject: enrolment visit (V0), inclusion visit (V1) and end of study visit (V2).

The Flow chart and the detailed of the study visit are detailed in appendix 18.3 and 18.4.

6.1.1. Eligibility

The eligibility of the subjects will be determined in accordance with the sites procedures and the following criteria will be checked by phone:

- 1/ Healthy male or female aged between 20 and 69 years (≥ 20 and ≤ 69 years)
- 2/ Metropolitan French origin for 3 generations
- 3/ Covered by a social security regimen or beneficiary of a social security regimen
- 4/ For women, not pregnant or breastfeeding
- 5/ BMI ≥ 18.5 and ≤ 32 kg/m² (Appendix 18.6)
- 6/ Access to a consistent means of telephone contact, which may be either in the home or at the workplace, land line or mobile
- 7/ Must understand spoken and written French

The site will use their subjects' registries in order to identify those subjects who meet the main eligibility criteria. The subjects' eligibility will be assessed and confirmed through a telephone interview.

In addition, the subjects could be recruited by means of an advertising campaign.

Subjects will be stratified according to age and gender in a 1:1 ratio. The stratification will be performed through a centralized stratification system. The stratification per group should be stopped once 100 subjects per strata were included. In addition, a randomization will be done at V1 to select 500 subjects who will complete the V2 (100 in each decade with 50% male and 50% female) and up to 500 subjects from these V2 subjects to perform a biopsy at V1.

A preliminary information meeting will take place upstream to the visit V0. At this visit the research will be explained by the investigator.

6.1.2. Enrolment visit (V0)

Subjects will attend visit V0 (enrolment visit) at the study centre to determine if they can be eligible for the study. The subject will have to be on an empty stomach for at least 6 hours.

Subject will receive an information consent form that will describe the research.

Subjects will be informed of the characteristics and the implications of the study both verbally and in writing by an investigator.

The subject will be informed and encouraged to participate in a non-interventional nutritional survey called “Etude Nutrinet-Santé” (www.etude-nutrinet-sante.fr) at least during the Labex study participation (between V0 and V2). The participation in this study will be optional (See below).

Nutrinet-Santé (Herberg et al. BMC Public health 2010) ⁽¹³⁾

Nutrinet study is a prospective cohort to study the relationship between nutrition and health and determinants of dietary patterns and nutritional status. It was launched in May 2009.

If subject agrees to participate in this study, they should register themselves via a web site (www.etude-nutrinet-sante.fr). All questionnaires and forms are made to be completed online, using a secure HTML interface where all conditions of data security and confidentiality are assured.

In accordance to the law n°2004-801 on August 6th 2004, before the data entry and computerization of the collected study data, the approval of the “Comité Consultatif pour le traitement Informatique en matière de recherche dans le domaine de la santé” and the authorization of the “Commission Nationale de l’Informatique et des Libertés” have been obtained.

Participant will be asked to complete the initial dietary intake questionnaires, questionnaire on physical activity, anthropometric data, life style and health status. The total duration for completing these questionnaires will be about 2h over the course of 23 days as described below:

- 3 questionnaires for collecting dietary intake data: 1h30
- 1 questionnaire for collecting:
 - physical activity data: 5mns
 - anthropometric data: 5mns
 - life style: 10mns
 - health status: 10mns

The data collected from this first step will be sent to Institut Pasteur for data handling and analysis. The data will be sent under pseudo-anonymised code (Labex enrolment number).

The subject will have the option to continue or withdraw from the Nutrinet Study at any time.

The subject will be informed that during the Labex-MI study they are not allowed to make any additional blood donation (e.g., EFS donation or other investigative studies).

The subject will be given time to discuss the information received before deciding to consent. Written informed consent will be obtained from the subject before any study procedure is performed.

The subject will be asked to sign the informed consent and a unique identification number (enrolment number) will be assigned and notified in the ICF and a complete pre-study evaluation will be conducted as described below:

- Demographic data;
- Clinical assessments;
 - Physical examination;
 - Vital signs measurements;
 - Blood pressure (2 supine measurements);
 - Heart rate;
 - Weight / Height;
 - Waist circumference;
 - Body temperature;
- Other assessments;
 - Past medical and surgical history;
 - Concomitant diseases;
 - Past (last 3 months) and current medications;
- Urine pregnancy test for women of childbearing potential;
- Electrocardiogram (12-lead electrocardiogram);
- Urinalysis;
- Blood sample collection for standard analysis (biochemistry, haematology, hemostasis, serologies): 20 mL (see appendix 18.5);
- Eligibility checks (inclusion / non-inclusion criteria).

The urine pregnancy test will be the first to be performed. In case of positive test, the subject is withdrawn from the study and no other tests will be performed.

The collected data will be recorded in the subject's e-CRF.

The investigator has to register the subjects into the French "Fichier des Volontaires se prêtant à la Recherche Biomédicale (VRB)" and check they have not reached the maximum amount of yearly cumulative compensation and that they are not in an exclusion period following a former participation in another research.

In case of any inclusion criterion not met or any non-inclusion criteria being present, the study must be stopped and the subject must be withdrawn from further study investigations.

At the end of the visit, the subject will be provided with material for stool collection that will be performed at home before or after returning at V1 (within 24 hours before the visit and up to 2 days after).

If subject agrees to participate in the Nutrinet-Santé Study, he/she will receive a card including the procedure and the enrolment number in order to register him/her to the study.

After receiving the results of the standard biological analysis, all the inclusion and non-inclusion criteria could be checked in order to confirm the subject inclusion. In case of non-inclusion criteria (due to standard biology results), the subject will be contacted for cancelling the inclusion visit (V1).

6.1.3. Inclusion visit (V1)

The inclusion visit (V1) will take place 4 to 14 days after (V0). The subject will have to be on an empty stomach for at least 6 hours. In addition the subject must not have made any physical exercise within 8 hours before the visit V1.

A unique inclusion number (randomization number) will be attributed to every included subject and the volunteer will be informed of the randomization outcome (i) to perform V2 with or without biopsy at V1 (ii) to perform only V1 without biopsy

After the subject has been included, the following procedures will be performed:

- Clinical assessments
 - Physical examination ;
 - Vital signs measurements ;
 - Blood pressure (2 supine measurements);
 - Heart rate;
 - Body temperature;
- Other assessments;
 - Lifestyle questionnaire including exercise habits ;
 - Concomitant treatments;
 - AE/SAE evaluation;
- Blood sample collection for (see appendix 18.5):
 - phenotypic assessment (baseline): 12mL
 - trial objectives: 75 mL
 - Genetic analysis (25mL);
 - TruCulture® - immune assays (50mL);
- Stools sample (collected at home within 24h before V1);
- Nasal swab;
- Skin punch biopsy (Appendix 18.2) for up to 500 subjects: for some subjects, the pose of strip or stitch will be made if clinically required. In case of stitches, they will be removed between 7 to 14 days after the biopsy and before V2.

Appropriate material and procedure for stool sampling will be given to the donor who will perform V2. Stool collection will be performed at home before or after returning at V1 (within 24hours before the visit and up to 2 days after).

The subject will be asked if he/she has joined the study Nutrinet - Santé.

The subject will be instructed to phone the center in case of any issue in biopsy site healing.

6.1.4. End of study visit (V2)

This visit will only occur for the subjects who will have been biopsied at V1. The visit (V2) will take place 28 days after (V1). A time windows of +/- 14 days is allowed then visit (V2) can take place maximum 42 days after (V1) and minimum 14 days after (V1).

The subject will have to be on an empty stomach for at least 6 hours. In addition the subject must not have made any physical exercise within 8 hours before the visit V1.

The following investigations will be conducted at the end of study visit:

- Clinical assessments;
 - Physical examination ;
 - Vital signs measurements;
 - Blood pressure (2 measurements);
 - Heart rate;
 - Body temperature;
- Other assessments;
 - Concomitant treatments ;
 - AE/SAE evaluation;
- Skin biopsy site examination, if applicable;
- Urine pregnancy test for women of childbearing potential;
- Blood sample collection for (see Appendix 17.5):
 - standard analysis (8mL) (see Appendix 17.5):
 - Haematology and CRP;
 - trial objectives:75mL (see appendix 18.5)
 - Genetic analysis (25mL);
 - TruCulture® - immune assays (50mL);
- Stools sample (collected at home within 24 h before (V2));
- Nasal swab;
- End of study assessment.

The urine pregnancy test will be the first to be performed. In case of positive test, the subject is withdrawn from the study and no other tests will be performed.

The subject will be asked if he/she has completed the study Nutrinet.

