8. Principal objective	To assess the determinants of immunologic variance within the general healthy population.
9. Secondary objectives	
To set-up a biobank of :
 
 • EBV transformed B cell lines • iPS cells from fibroblasts of healthy human individuals
10. Primary outcome	
To identify factors (genetic, immunological and environmental) that contributes to the observed heterogeneity in immune responses (individual and population levels).
 
 • To characterize the naturally occurring genetic variability of human response using whole genome sequencing and SNPs haplotyping. • To determine and measure cytokine/chemokine stimulated by 40 pattern-recognition receptors agonists (PRR agonists) or immune

	
stimulators.
 
 • To characterize commensal microbiota (nasal swab and stools samples) in the study population • To evaluate the metagenomic architecture of the population based on sequence analysis of bacterial, fungal and viral populations in fecal and nasal samples. • To associate immune response with nutrition data. • To associate immune phenotype variance with genetic polymorphisms and enterotype.
11. Secondary outcomes	Determination of genotype-to-phenotype associations at a mechanistic level.
12. Subjects	Healthy adults subjects
13. Number of subjects	
Around 1200 subjects will be enrolled at V0 to include 1000 subjects at V1 among whom 500 will complete the visit V2 and, on these 500, up to 500 will perform a biopsy at V1.
 
At V1, subject recruitment will be stratified by:
 
 • Gender (50%/50%): 500 males / 500 females • Age: 5 decade strata (20% in each): 200 subjects/decade • 100 subjects by gender by decade strata • Age (≥ 20 and ≤ 69 years) • Biopsie: (10% in each decade and 50% by gender) 
In the event of a premature withdrawal, the subject will be replaced by a subject of the same gender and age decade, to ensure a number of 500 complete observations at V2 with 100 subjects in each decade strata and 50 subjects in each gender.

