3. METHODOLOGY

3.1. Study design

- Type of study: Clinical interventional study.
- Number of subjects included: 1000 healthy volunteers.
- Investigational product: Not applicable, no investigational product
- Experimental design: single center study (1 center) in France
- Visit/contact schedules: 3 scheduled visits
 - V0: 1200 subjects

-
- V1: 1000 subjects (500 performing V2 with or without biopsy at V1 on the draw by lot)
 - V2: 500 subjects having or not performed biopsy at V1
 - Data collection: data collected by investigator on an electronic CRF
 - Biological sample: blood, stools, nasal swab and skin biopsy will be collected for the evaluation of the trial objectives
 - Duration of the study (FSFV – LSLV): Approximately 1 year. All subjects will be enrolled within 10 months after study set-up. For each individual subject performing the biopsy and for each individual performing V2 without biopsy at V1, the duration of the study will be around 8 weeks (56 days) from V0 to V2. For each individual subject only performing V1, the duration of the study will be around 2 weeks (14 days) from V0 to V1.
 - Statistical analysis: data handling and statistical analysis will be performed at the Institut Pasteur.

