7. STUDY COMPLETION AND SUBJECT REMOVAL FROM THE STUDY

7.1. Study completion

Subjects randomized to perform V2 (with biopsy or not at V1) will be considered to have completed the study after having attended visit V2.

Subjects randomized to only perform V1 will be considered to have completed the study after having attended visit V1.

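### Protocol section 6.1.4 limits V2 to biopsied subjects, contradicting the rest of the protocol, which plans V2 for 500 randomised subjects with or without biopsy

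*Protocol*

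**What the plan says.** Section 6.1.4 opens with a restriction: "This visit will only occur for the subjects who will have been biopsied at V1". Further down, its list of V2 procedures includes "Skin biopsy site examination, if applicable", which makes sense only if some V2 attenders have no biopsy site.

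Four other places in the protocol give the number at V2 and do not require a biopsy of everyone:

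- Synopsis, number of subjects: of the 1000 at V1, "500 will complete the visit V2 and, on these 500, up to 500 will perform a biopsy at V1". Withdrawn subjects are replaced "to ensure a number of 500 complete observations at V2 with 100 subjects in each decade strata".
- Section 3.1: "V2: 500 subjects having or not performed biopsy at V1".
- Section 4.1, table footnote: "In case less biopsy is performed, 500 subjects will even though performed V2 without biopsy at V1".
- Section 6.1.1: randomisation at V1 selects 500 for V2, and the biopsy subjects, at most 500, are taken from among those.

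Four more provide for V2 without biopsy but give no number:

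- Synopsis, subject compensation: a separate 250 euro tier for V1 plus V2 without biopsy.
- Section 3.2.3: one participation time for V2 subjects, biopsied or not.
- Section 6.1.3: one of the two randomisation outcomes is V2 regardless of biopsy.
- Section 7.1: completion is defined for "Subjects randomized to perform V2 (with biopsy or not at V1").

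Section 6.1.4 also states the exercise rule for the V2 visit as "the subject must not have made any physical exercise within 8 hours before the visit V1". Non-inclusion criterion 6 in section 4.3 applies that rule before V1 and before V2.

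**The concern.** Section 6.1.4 is the instruction a site would follow when running V2. Its opening sentence makes biopsy the condition for attending, whereas everywhere else the condition is the draw at V1. The two conditions select different people as soon as one subject drawn for V2 is not biopsied, and the footnote in 4.1 shows that the sponsor foresaw this.

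A subject drawn for V2 but not biopsied would, under 6.1.4, not be seen again. Under 7.1 that subject could not complete the study, and 7.2 treats stopping before the V2 assessments as a withdrawal that calls for replacement. The sentence therefore conflicts with the completion and replacement rules as well as with the planned count.

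What is at stake is the size and make-up of the V2 group, which section 1.3 describes as the validation sample. It could fall below the 500 complete observations that the synopsis seeks, and it would contain no unbiopsied donors.

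**Working it through.** **Inputs.** The table in 4.1 has 5 decades, 2 sexes, and 50 + 50 subjects per cell at V1, of whom 50 go on to V2. Section 12.2 gives the precision figures. The number of biopsies, B, is capped at 500 but not fixed, so values below 500 are assumptions.

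**Reproducing the plan's figures.**

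- V1: 5 × 2 × (50 + 50) = 1000. V2: 5 × 2 × 50 = 500. Both match the table.
- Half-width of a 95% CI for a mean, in SD units, is 1.96/√n: 1.96/√1000 = 0.062 and 1.96/√100 = 0.196, stated as 0.062 and 0.20.
- For a percentage it is at most 1.96 × √(0.25/n): 0.031 for n = 1000 and 0.098 for n = 100, stated as 0.03 and 0.10.

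The section 12.2 formulas are therefore confirmed and can be applied to V2 counts.

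**Applying the two rules.** Under 6.1.4, V2 size = B, with no unbiopsied donors. Under the other sections, V2 size = 500, with 500 − B unbiopsied donors. B counts every biopsied subject, including replacements, so replacement closes the gap under 6.1.4 only if the replacement is biopsied.

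| B (assumed) | V2 under 6.1.4 | Shortfall from 500 | Unbiopsied at V2 under the other sections | Half-width under 6.1.4, all V2 | Per cell (B/10) | Half-width per cell |
|---|---|---|---|---|---|---|
| 500 | 500 | 0 | 0 | 0.088 SD | 50 | 0.28 SD |
| 450 | 450 | 50 | 50 | 0.092 SD | 45 | 0.29 SD |
| 400 | 400 | 100 | 100 | 0.098 SD | 40 | 0.31 SD |
| 300 | 300 | 200 | 200 | 0.113 SD | 30 | 0.36 SD |

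The cell figures are 1.96/√50 = 0.277, 1.96/√45 = 0.292, 1.96/√40 = 0.310 and 1.96/√30 = 0.358. They assume that biopsies are spread evenly over the ten cells.

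**Reading the table.** At B = 500 the two rules give the same people and the same count. This is the case shown in the main rows of the 4.1 table, where every biopsied row has 50 at V2 and every unbiopsied row has 0. Below 500 the rules diverge by exactly the number of missing biopsies.

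**The case against.** The strongest reply is that the protocol largely answers the question itself. V2 attendance is allocated at V1 and the subject is told the outcome then, before 6.1.4 comes into play. The footnote in 4.1 covers the case of fewer biopsies, the payment schedule covers V2 without biopsy, and 6.1.4 itself makes the biopsy-site check conditional. With so much contrary text, misapplication is possible but not likely. That stands, and it lowers the severity. It does not make the sentence correct: 6.1.4 says *only*, and no reading reconciles that with the other sections once a V2 subject is unbiopsied.

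A reader might also infer more than the documents support:

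- *That V2 will fall short.* It falls short only if 6.1.4 is followed and fewer than 500 biopsies are done. At 500 the shortfall is zero.
- *That this sentence is what confounds V2 with biopsy.* If all 500 biopsies are done, the other sections also make the V2 group and the biopsied group identical. Correcting 6.1.4 leaves unbiopsied donors at V2 only when B < 500. For the same reason, adjusting for biopsy status is no general remedy, since it is constant among V2 donors when all are biopsied.
- *That V2 would be selected by willingness to be biopsied.* Sections 4.1 and 6.1.1 describe selection by lot, and no section attributes a shortfall to refusals.
- *That a stated precision is missed.* The figures in 12.2 are for 1000 donors and 100 per cell, which are V1 numbers. No precision or power is claimed for V2, and no listed outcome is a change from V1 to V2.

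The exercise wording is a separate and smaller slip. It repeats the wording of 6.1.3, and criterion 6 already extends the restriction to V2.

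**Conclusion.** The contradiction is real and in the current text. Section 6.1.4 conflicts with four places that set V2 at 500 without requiring biopsy of all, with four more that provide for V2 without biopsy, and with its own procedure list.

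The consequence is conditional. If 6.1.4 were followed and B < 500, V2 would lose 500 − B donors and contain no unbiopsied ones. The loss of precision per cell, from 0.28 SD to 0.31 SD at B = 400 or 0.36 SD at B = 300, is an illustration. It rests on assumed biopsy counts, an even spread over cells and the section 12.2 formula, not on a target that the protocol sets for V2. The V1 sample of 1000 is unaffected.

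This is a should-fix clarification of an internal inconsistency.

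**What to change.** Reword the opening sentence of 6.1.4 so that it follows the randomisation: V2 takes place for the 500 subjects randomised at V1 to perform it, whether or not a biopsy was taken.

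In the same section, reconcile the exercise restriction, which refers only to V1, with non-inclusion criterion 6, which covers both visits.

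The cost is two sentences in a protocol clarification. No subjects, visits or procedures are added, because 500 V2 visits are already planned.
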